The sample population consists of a convenience sample that is participating in a pilot study. This study will focus on nonpregnant healthy adult (ages 18+) community members who walk the Tanglewood Trail on Saturdays, June-September 2018 and at Letcher County Recreation Center October 2018 – February 2019. Any interested community members who are 18 years or older, nonpregnant and able to voluntarily give their consent are welcome to join the study. Seventy-five participants will be recruited to participate in this project in Whitesburg ("walking group"), and seventy-five control participants will be recruited in Harlan ("control group"), who will only receive monthly nutrition education via e-mail or home mail. An information session for any potentially interested individuals will be held by the UK program manager with the help of the community leader following IRB approval. The 75 walking group participants will meet at the Housing Authority at a designated time each Saturday. When they arrive, they will be signed in by a community leader and receive a farmer's market voucher (see attached) for \$10. They will walk as a group to the farmer's market and hand their voucher to the market manager, who will give them \$10 in tokens to purchase fruits and vegetables at the market. The voucher will have two sides: one side will ask participants to check off what fruits and vegetables they ate over the past week, the second side will ask how participants used what they purchased at the market last week (ie. How much was eaten fresh vs. preserved) and how many steps they took over the past week, tracked using a pedometer provided at the baseline measurements in May 2018. They will turn the filled-out voucher in as they leave the market. During the meal preparation portion of the study, participants will complete weekly meal evaluation sheets. The walking group will receive 1) Education - nutrition education weekly via a combination of nutrition posts on Facebook (2/mo June – Sept), recipe and phytonutrient cards that includes a video recipe demonstration (1/mo), and recipe samples with cards (1/mo). Post-farmer's market: 1 weekly recipe demonstration (YouTube and offered live), recipes with nutrition/phytonutrient information to accompany meals (Oct – Jan); 2) Vouchers- weekly \$10 farmer's market vouchers (June – Sept), weekly \$20 healthy meal vouchers (Oct – Jan); 3) PA - 1 day/week community walk along Tanglewood Trail (June-Sept) and admission to Recreation Center (Oct – Jan), and 4) Activity trackers - a 3DTriSport pedometer. The 75 control group participants will receive monthly nutrition education via their choice of e-mail or home mail. Nutrition education will focus on phytonutrients, the importance of fruit and vegetable intake, how these factors might protect them from environmental pollutants, and healthy cooking. This nutrition education will also be provided to walking group participants via Facebook. Walking group participants will also have access to monthly Farmer's Market samples of Plate it Up Kentucky Proud recipes and recipe cards. No participants will receive medications – neither real nor placebo. Data for both the walking group and control group will be a time series collection of blood pressure, finger-stick total cholesterol, LDL, HDL, triglycerides, hemoglobin A1c (cardiocheck meter), height, weight, waist circumference, carotenoid status (carotenoid RS, which is a non-invasive instrument that is a reliable indicator of fruit and vegetable intake (see attached), Newest Vital Sign (NVS) rapid screening test for health literacy, and a survey (see attached). Measurements will be taken and surveys collected three times – baseline data will be collected in May 2018, mid-point data collected late September/early October 2018, and follow-up data collected in February 2019. Only walking group participants will receive pedometers and report weekly steps to the community leader at the Farmer's Market (June through September) or CANES Kitchen (October through February). Finger stick tests will be conducted by University of Kentucky employees who have completed all necessary biohazard training (see attached IBC approval and certificates of completion). Lysol wipes will be available to wipe down equipment as needed. Hand sanitizer will be provided to each researcher to use between glove changes. Gloves will be changed between each participant. Heat packets will be available for participants with cold hands to make the finger stick go faster and easier. Band-Aids will be provided after each stick. Lancets will be used to take the finger stick and all materials will be disposed of in sharps containers. All sharps containers will remain sealed until the research team returns to the University of Kentucky that same day to dispose of the sharps containers. Additionally, focus groups with walking group participants will be conducted in October 2018 and February 2019. Questions for the focus groups will be formulated out of 5-10 informant interviews conducted in July (with each interview lasting approximately 30 minutes – 1 hour). Participants for both interviews and focus groups will be recruited with the help of the market manager and community leader, and all participants will be informed that they are participating in the interviews and/or focus groups for research purposes and sign a consent form. Questions asked will assess program use, attitude/behavior change over the course of the program, social capital, and social cohesion.

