Based on walking group numbers from summer 2017 we anticipate a maximum enrollment of 75 walking group participants (18+ years old, nonpregnant) and 75 control participants. Previous research in Letcher County suggests the majority of participants will be white, ages 18-65, both male and female, of moderate health status. A prerequisite for participating in this study is the ability to walk 1 mile (assessed using the Exercise and Sports Science Adult Pre-Exercise Screening Tool, Stage 1 – see attached), nonpregnant, pre-supposing a baseline health status. Any interested community members over the age of 18 and in moderate or good health will be included. Since our focus is on changes in rates of chronic disease in adulthood, children will be excluded from study participation (but may walk with their parents). Institutionalized adults, pregnant adults, adults with impaired consent capacity, and prisoners will be excluded. No one will be excluded based on sex/gender or racial/ethnic identity. Seventy-five participants in Harlan County will be enrolled in the control group with the same inclusion/exclusion criteria as the walking group. Interview and focus group participants will include volunteers from the walking group. All participants will be informed that the interviews and focus groups are for research purposes, and sign a consent form.

Attachments

Subject Recruitment Methods & Privacy: Describe plans for the identification and recruitment of subjects, including how the population will be identified, and how initial contact will be made with potential subjects by those having legitimate access to the subjects' identity and the subjects' information. Describe the setting in which an individual will be interacting with an investigator. If applicable, describe proposed outreach programs for recruiting women and minorities as participants in clinical research.

Please note: Based upon both legal and ethical concerns, the UK Medical Institutional Review Board (IRB) will not approve finder's fees for research studies.

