All study personnel that will obtain consent are listed in Form A. Participants will be told they can decide to stop their participation at any time. The consent form will be read to any study participants with visual issues. UK study personnel will speak to study participants at an appropriate volume to be heard by study participants. Study personnel will ask if they are speaking loud enough, they will tell study participants to let them know when they need to speak up or slow down or repeat a question, and study personnel will be in tune to signs of study participants straining to hear. Consent will be obtained before physical measurements or survey data is collected. To obtain consent the UK study personnel will ask potential participants if they would like to participate in a research study that involves asking them questions about their health and diet and will also involve education material on phytonutrients, the importance of fruits and vegetables, how these factors might protect them from environmental pollution, and healthy cooking. They will be told their participation is completely voluntary, and extend beyond the farmer's market season. All consenting participants will be given the opportunity to sign a photo release. Whether they sign or not does not impact their participation in the study. All consenting participants will complete the Adult Pre-Exercise Screening Tool to assess their ability to take part in the walking group. They will also be told their survey answers will not be reported individually or with their name, but as anonymous aggregated data. Additionally, they will be told their participation is voluntary and they can withdraw from the study at any time and they do not have to answer any questions that they are not comfortable answering. If the participant agrees the consent form will be given to them and their signature obtained. The participant will be given a copy of an investigator-signed consent form. The UK study personnel will ask if the participant would like to move elsewhere to complete the survey and anthropometric/biological data collection. Study personnel will also explain that the consent forms and surveys will be stored separately in a locked drawer in the PI's locked office and that an electronic file will be created that lists their name and survey code. This list will be destroyed following the collection and entry of post-survey data. Any electronic files generated from this study will be stored on a password protected computer. Obtaining consent and completing the survey will take approximately 15 minutes. An additional 30 minutes will be needed to complete the anthropometric and biological measurements. The midpoint and post data will be collected in the same manner as the pre data. The UK study personnel will offer the same explanation of the survey and anthropometric/biological measurements and the same procedures will be followed, consent however will not be obtained again. The midline and post-surveys will contain a cover sheet that has a place to record the participant's name. The next page will be where the first question is listed and a space for the survey code to be recorded. Once the survey has been coded the cover sheet will be removed from the midline and post-surveys and shredded once all data has been entered electronically. At time of recruitment, interview and focus group participants will be told they are participating in an interview or focus group for research purposes. At the time of each interview and at the time of the focus group, the researcher will explain again that the interview and focus groups are being conducted for research purposes, and no one will be forced to participate or answer any questions they do not wish to answer. All participants who agree to participate will sign a consent form.

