
[Back to Top](#)

Research Procedures: Describe the research procedures that will be followed. Identify all procedures that will be carried out with each group of subjects. Differentiate between procedures that involve standard/routine clinical care and those that will be performed specifically for this research project.

Following IRB approval, beginning in May 2018 community members will show up to a designated location approximately 1 kilometer

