Participation in every aspect of the intervention is voluntary. Participants do not have to respond to any survey or focus group questions that they are uncomfortable answering or participate in any anthropometric or biological measurements they are uncomfortable with. All identifiable data will be transported directly to the program manager's locked office on UK's campus. The program manager will keep any identifiable data with her at all times until it is locked in a drawer in her locked office. The program manager and primary investigator will be the only two with access. When identifiable data (names) is being collected it will be on the cover sheet or consent form of a survey and will be detached from survey data that will include a code that is linked to the participant. At the end of the study, the cover sheets will be deleted and consent forms will be stored separately from the surveys in a locked drawer in the PI's locked office. The electronic list containing the names and survey codes will be deleted once all post-survey data is entered, which will be entered within a month following collection. However, the assigning of codes, and generating the electronic document that lists codes and names from surveys will occur the day of data collection at UK. The study population consists of adults ages 18 years or older who are in good enough health to walk 1 kilometer to the farmer's market. Finger stick tests will be conducted by University of Kentucky employees who have completed all necessary biohazard training and have received training by a Registered Dietitian in how to use the meters. Lysol wipes will be available to wipe down equipment as needed. Hand sanitizer will be provided to each researcher to use between glove changes. Gloves will be changed between each participant. Heat packets will be available for participants with cold hands to make the finger stick go faster and easier. Lancets will be used to take the finger stick and all materials will be disposed of in sharps containers. All sharps containers will remain sealed until the research team returns to the University of Kentucky that same day to dispose of the sharps containers. All labs will be conducted on site and materials disposed of as indicated above. There are minimal and short term risks associated with finger sticks, such as initial pain and tenderness for at least a day or two. There are no known risks of using a carotenoid scanner.

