If yes, check below all that apply and attach the applicable document(s): [?](#)

- HIPAA De-identification Certification Form
- HIPAA Waiver of Authorization

[Attachments](#)

STATISTICAL ANALYSIS PLAN

This study will recruit approximately 150 participants, who will be divided into walking or non-walking groups to assess dietary behavior. Outcomes will compare the change in fruit and vegetable intake, health and exercise at baseline, 4 months and 8 months using survey metrics. Significance will be determined using a two-way ANOVA with a post-hoc Tukey's t-test; $p<0.05$.

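### No described step brings back walkers who stop attending, and the planned ANOVA uses whoever returns, so the two arms may be lost by different mechanisms.

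*Combined protocol and SAP*

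**What the plan says.** **Sample.** The Statistical Analysis Plan states: "This study will recruit approximately 150 participants, who will be divided into walking or non-walking groups to assess dietary behavior". Study Design says "Seventy-five participants will be recruited to participate in this project in Whitesburg", and Study Population adds "Seventy-five participants in Harlan County will be enrolled in the control group with the same inclusion/exclusion criteria as the walking group".

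**Follow-up.** Study Design and Data Collection schedule three rounds for both groups: May 2018, late September or early October 2018, and February 2019. No attendance condition is attached. Informed Consent Process says "The midpoint and post data will be collected in the same manner as the pre data"; the sentence after it covers the explanation given, the procedures and the absence of a second consent. For the May round, Research Procedures says "community members will show up to a designated location approximately 1 kilometer" from the market. No follow-up site is stated for either county.

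**Leaving and returning.** Participants may withdraw at any time (Informed Consent Process), and under Safety Precautions they need not "participate in any anthropometric or biological measurements they are uncomfortable with". Payment offers all participants a USD 10 gift card at each follow-up round.

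**Contact.** Walkers sign in on Saturdays and receive vouchers there. From October they report steps and receive meals at CANES Kitchen. They also have a Facebook group. Controls receive monthly e-mail or home mail.

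**Analysis.** "Significance will be determined using a two-way ANOVA with a post-hoc Tukey's t-test", at the 0.05 level. No analysis population, dropout allowance or missing-data method is given. The hypothesis in the opening background section concerns adults who attend regularly, whereas the specific aims refer to participants in the active intervention.

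**The concern.** A walker who stops coming leaves the main channel through which the plan describes contact and benefits. A control cannot lapse in that way. If walkers who lapse are also those whose diet, activity or weight is going less well, the walkers measured at 4 and 8 months are a favourable subset. The control arm is thinned by some other process. The difference between arms then contains a selection effect that looks like programme benefit.

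Nothing in the analysis plan would detect or limit this. Whatever form the ANOVA takes, the follow-up means come from returners. A background hypothesis framed around regular attenders adds to the risk that attenders end up compared with all returning controls. A missed visit cannot be recovered afterwards.

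**Working it through.** **1. The plan's own figure.** 75 + 75 = 150, which agrees with the SAP. Power, effect size, SD and dropout are not given, so no sample-size calculation can be reproduced. For scale, at an assumed 80% power and two-sided 5%, the detectable difference is sqrt(2/75) × (1.960 + 0.842) = 0.163 × 2.802 = 0.46 SD.

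**2. What attendance carries.** June to September 2018 has 18 Saturdays, so vouchers come to 18 × 10 = USD 180. Meals come to 16 × 20 = USD 320. Gift cards are 2 × 10 = USD 20. A walker who attends throughout receives about USD 520, of which USD 500 comes with attending and USD 20 with being measured. A control receives USD 20, all of it for being measured.

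**3. Illustration of the bias.** Assumed: no true effect; the same share d lost in each arm; controls lost at random; the lowest-attending walkers lost; attendance correlated rho with change (normal model, SD of change = 1).

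- Bias = rho × phi(z_d)/(1 − d). At d = 0.25, phi = 0.318 and 0.318/0.75 = 0.424.
- SE = sqrt(2/(75 × 0.75)) = sqrt(2/56.25) = 0.189.

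| rho | bias (SD) | bias/SE | false positives, two-sample test of change |
|---|---|---|---|
| 0 | 0 | 0 | 5% |
| 0.2 | 0.085 | 0.45 | 7–8% |
| 0.3 | 0.127 | 0.67 | 10% |
| 0.5 | 0.212 | 1.12 | 20–21% |

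Over rho 0.2 to 0.5, the bias is 0.06–0.14 SD at 15% loss and 0.13–0.32 SD at 40% loss. Against the 0.46 SD detectable difference, 0.085 to 0.212 is about 19% to 46%.

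**4. If controls are also selected, half as strongly.** At 30% loss the false-positive rate falls from 12.1% to 6.7% (rho 0.3) and from 26.0% to 10.1% (rho 0.5).

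**5. These rates are not those of the named ANOVA.** An ordinary two-way ANOVA with no within-person term gives the group-by-time contrast an SE of sqrt(2/56.25 + 2/75) = 0.249 outcome SDs. At a baseline to follow-up correlation r, the SD of change is sqrt(2(1 − r)). The rho 0.3 bias is therefore 0.127 outcome SDs at r = 0.5 (ratio 0.51) and 0.127 × 0.632 = 0.080 at r = 0.8 (ratio 0.32). Both ratios are below 0.67, and that SE also overstates the true spread because it ignores pairing. The test would reject less often, usually below 5% when simulated in these settings. The estimate stays biased.

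**6. Which remedies work in this scenario (rho 0.3, 25% loss).**

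- *No change assumed for lost walkers:* 0.75 × 0.127 + 0.25 × 0 = 0.095. Only a quarter of the bias goes.
- *Attendance used:* measured walkers sit 0.424 SD above the arm's mean attendance. Regressing change on attendance and averaging over all 75 gives 0.127 − 0.3 × 0.424 = 0.
- *Size of shift a tipping-point analysis must reach:* all enrolled average zero, so lost walkers average −(0.75 × 0.127)/0.25 = −0.381. That is 0.127 + 0.381 = 0.51 SD below measured walkers. By the same arithmetic it is 0.34 at rho 0.2 and 0.85 at rho 0.5.

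**The case against.** **The follow-up site.** A reader might infer that walkers are re-measured where the walk starts, because the May location and the Housing Authority are both about 1 kilometer from the market. The documents do not support this. The May location is not named. The wording about collecting data in the same manner is followed by explanation, procedures and consent, not place. Subject Recruitment Methods & Privacy describes baseline as an event to which people are invited, held before the June walks begin. By February the walking has moved elsewhere. The answer under Resources and the consent pages are not in the available text and may name a site. This objection stands in full.

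**Controls.** A reader might also infer that controls are an unselected comparison. They are volunteers recruited through a community leader, they must return to be measured, and they can decline or withdraw. What remains is only that the loss mechanisms may differ.

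**Existing retention measures.** Gift cards go to everyone at both rounds, and walkers can be reached through Facebook. Both should help. Neither is described as a way of following up people who have lapsed, and neither replaces a missing-data method.

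**The numbers.** Loss, correlation and random control loss are all assumed, and the error rates belong to a simpler test than the one planned. That is correct, and it is why the figures serve only as an illustration.

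**Conclusion.** The point holds in a limited form. The plan sets three measurement rounds for everyone, but the available text gives no procedure aimed at walkers who stop attending, no analysis population and no missing-data method. Attendance-related loss can therefore bias the comparison, most plausibly in favour of the programme.

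The size cannot be derived from the documents. Under the assumptions in the working, 25% loss gives 0.09 to 0.21 SD. The bias is smaller if controls are selected too, and zero if loss is unrelated to change. The 7 to 21% false-positive range applies to a two-sample comparison of change scores. It should not be read as the error rate of the planned ANOVA.

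Nothing here shows that bias will occur, and no claim is made about where follow-up takes place. The change is worth making because it is cheap and must be made before the follow-up rounds.

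**What to change.** 1. **Protocol.** State that everyone enrolled in both counties is invited to the midpoint and February rounds by mail, e-mail or phone, whether or not still walking, and that the gift card does not depend on attendance. State the follow-up site for each county. In the same edit, reconcile the 2017 post-data dates in Research Procedures with the 2018–2019 schedule elsewhere.

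2. **SAP, main analysis.** Replace the ANOVA on returners with a repeated-measures mixed model, or multiple imputation by arm. Include everyone enrolled, in the group they joined, with all available visits. Use walkers' recorded session attendance as an auxiliary variable, in the imputation or a joint model. It should not be a covariate in the group comparison, because it arises after enrolment. The Saturday sign-in supplies it for the summer; keep an equivalent log from October. Report retention by arm, visit and attendance.

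3. **SAP, sensitivity.** Do not treat survival under a no-change imputation as proof of robustness. Use a delta-adjusted (tipping-point) analysis in which unmeasured walkers do progressively worse than measured ones, over a range covering at least the 0.34 to 0.85 SD shifts above. If the result is fragile, limit the claim to participants who returned.

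**Cost.** A few reminder contacts, an attendance log and a little more analysis. The estimate may be smaller or less precise. The attendance adjustment also extrapolates to low attenders who were not measured, which is why items 1 and 3 are still needed.
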